##### Developmental Process

Of the 300 eligible students, 145 agreed to participate. Block randomization was used for the random assignment of students to the experimental group (EG) and control group (CG). The unit of randomization was small groups (13-16 students/group), with all enrolled students assigned accordingly. Block randomization was performed using a random number generator, assigning 5 blocks to the experimental group (80 students) and 5 blocks to the control group (65 students).

Both groups (EG and CG) received BTI training in a brief format of 2.5 hours in groups of 13-16 students. The content included 1) general information and epidemiology of smoking, 2) passive smoking, 3) evidence of the effectiveness of smoking cessation interventions, and 4) the WHO's approach to smoking in Primary Care based on the 5 As and 5 Rs model to help patients quit smoking (World Health Organization, 2014). This model outlines the five main steps of the 5 As (Ask, Advise, Assess, Assist, and Arrange) for providing brief interventions in primary care and the 5 Rs (Relevance, Risks, Rewards, Roadblocks, and Repetition) to be addressed for a smoker who is not ready to quit at that moment.

The methodology included a phase of evaluating the students' learning using the Videotape Objective Structured Clinical Examination (VOSCE). Students were shown 3 recorded clinical scenarios (video-problems) with standardized patients in which a nursing professional performs a brief tobacco intervention (BTI) on a patient visiting a primary care clinic, following the 5 As and 5 Rs model. The videos depicted common errors in this type of intervention, and students were required to detect them using the validated BTI-St® assessment tool. The scenarios included the patient was not ready to quit smoking (scenarios 1 and 2) and was ready to quit (scenario 3).

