The data collection protocol was similar in both the EG and CG, with five measurements conducted each time after viewing the 3 video-problems and assessing learning through the BTI-St®. At baseline, before BTI training (T0); followed by training in BTI in Primary Care (T1). Subsequently, in the experimental group, an expert instructor conducted a structured debriefing lasting 10-15 minutes for each clinical scenario, whereas no further intervention was provided in the control group. At the end of the first day, all participants viewed the videos and completed the tool again (T2). At three and nine months, students viewed the videos and measurements were taken at T3 and T4, respectively.

The debriefing used had the following characteristics: short ( $\leq 15$  minutes), educator present, educator with debriefing experience, the context was related to health management or decision-making, and the method used was the plus-delta tool, which asks participants to reflect on the simulation event and evaluate their performance by identifying strengths and areas for improvement.

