## Method of Measurement

To assess the change in learning regarding brief tobacco cessation counseling among nursing students, the Brief Tobacco Intervention BTI-St© tool was used, incorporating the standardized patient videos described earlier. This instrument is based on a criterion-referenced or competency test model, enabling an objective evaluation of students' BTI performance and identifying learning deficiencies. It is presented as an algorithm consisting of 23 dichotomous items organized according to the 5As and 5Rs model and has demonstrated adequate validity and reliability (Ramos-Morcillo et al., 2022). Students must view a recorded clinical scenario and determine whether the brief intervention criteria for smoking cessation are met. Responses are corrected according to the gold standard defined during the scenario validation, with item scores ranging from 0 (incorrect) to 1 (correct). The maximum total score for each scenario ranges from 0 to 1 point if the student answers all items correctly.

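### Only the experimental arm is debriefed on the three videos that then serve as the test at T2, T3 and T4, so the design cannot distinguish transferable learning from recall of those videos.

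*Combined protocol and SAP*

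**What the plan says.** The protocol describes a single set of test material. "Students were shown 3 recorded clinical scenarios (video-problems) with standardized patients" (Developmental Process), and the student's task is to find the errors built into them. The data collection plan has "five measurements conducted each time after viewing the 3 video-problems and assessing learning through the BTI-St" tool. Scoring is tied to the particular video: "Responses are corrected according to the gold standard defined during the scenario validation" (Method of Measurement).

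The arms part after T1. Experimental students are debriefed: "an expert instructor conducted a structured debriefing lasting 10-15 minutes for each clinical scenario". For the other arm the protocol states only this: "whereas no further intervention was provided in the control group". T2 takes place at the end of that same day with the same videos. For follow-up, "At three and nine months, students viewed the videos and measurements were taken at T3 and T4, respectively".

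The debriefing is described as a plus-delta exercise, in which participants look back on the event and on their own performance. Method of Measurement presents the outcome as a change in learning of brief tobacco counselling. The Aim asks about the effectiveness of debriefing and how it progresses to 3 and 9 months. No parallel scenario, undebriefed scenario or debriefing on other material for controls is described.

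**The concern.** The intervention is delivered on the items of the outcome test, and in one arm only. Practice from repeated viewing is not the difficulty, because both arms view the videos on the same schedule. The difficulty is expert-led discussion of each test video. It is part of the treatment contrast, so randomisation does not balance it, and the repeated-measures ANOVA cannot separate it from learning.

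A student who has learned the 5 As and 5 Rs better should score higher on these videos. So should a student who only remembers what was discussed about these consultations. The first would be expected to do better with a new patient and the second would not. All three scenarios were debriefed, so the whole outcome is open to both explanations. What is at stake is the meaning of a positive result: better learning of the brief intervention, or better error detection in three familiar videos. The same question applies to any persistence claimed at T3 and T4.

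**Working it through.** **1. The plan's own figure.** The only quantitative claim is 100% power for the group-by-time interaction (Sample and Setting: 2 × 65 students, 5 measures, 5% level, effect standard deviation 1). With noncentrality N × M × σ_AB² / [SD² × (1 − ρ)] = 130 × 5 × 1 / [SD² × (1 − ρ)], power is 1.000 for an SD of 1 or 2 at every correlation tried (0, 0.5, 0.8) and every sphericity factor tried (1, 0.5, 0.25). The figure reproduces under those assumed values, but it says nothing about what an arm difference would mean.

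**2. Exposure to the test videos.**

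| Step | Experimental | Control |
|---|---|---|
| T0, T1 | same three videos, fixed key | same |
| Between T1 and T2 | expert debriefing on each of the three videos | nothing further |
| T2 (same day) | same three videos | same |
| T3, T4 (3 and 9 months) | same three videos | same |

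The number of viewings is equal. Discussion of the videos differs, and it covers 3 of 3 scenarios.

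**3. Size of a recall-only gap.** The documents give no means, so the inputs are assumptions. Suppose controls score p at T2. Suppose experimental students have no extra transferable learning, but recall the right answer for a share r of the items they would otherwise miss. Then

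gap = r × (1 − p).

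- Low end, r = 0.25 and p = 0.8: 0.25 × 0.2 = 0.05.
- High end, r = 0.75 and p = 0.6: 0.75 × 0.4 = 0.30.

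The tool has 23 items, and the number answered per scenario is not given. If all 23 are answered, one item is worth 1/23 = 0.043, so the range is 0.05 × 23 = 1.15 items to 0.30 × 23 = 6.9 items.

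**4. Would such a gap be detected?** Take a simple two-group comparison with 65 and 80 students (Developmental Process), two-sided 5%, with students first treated as independent. The score SD is assumed.

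- Standard error = SD × √(1/65 + 1/80) = SD × 0.167.
- Difference detectable with 80% power = (1.96 + 0.84) × standard error.
- Power for a gap d = Φ(d / standard error − 1.96).

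Randomisation was by small group. With 145/10 = 14.5 students per group and an assumed intracluster correlation of 0.05, the design effect is 1 + 13.5 × 0.05 = 1.675. The detectable difference is multiplied by √1.675 = 1.29.

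| Assumed SD | Detectable, independent | Detectable, clustered | Power at gap 0.05 (independent) | Power at 2 recalled items, 0.087 (independent) |
|---|---|---|---|---|
| 0.10 | 0.047 (1.1 items) | 0.061 (1.4 items) | 0.85 | 0.999 |
| 0.15 | 0.070 (1.6 items) | 0.091 (2.1 items) | 0.51 | 0.94 |
| 0.20 | 0.094 (2.2 items) | 0.121 (2.8 items) | 0.32 | 0.74 |

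Clustering lowers the two power columns. Recall of two or three items per video could be enough for significance, but the low end of the range often would not be.

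**The case against.** The strongest reply is that discussing the event just experienced is what debriefing is. The Aim asks about debriefing after an objective evaluation, and using the same validated scenarios keeps the five time points comparable. The documents do not expressly claim transfer to unseen consultations. This stands in part: the randomised contrast of debriefing with no debriefing is a legitimate contrast for performance on these videos. It does not carry that contrast over to learning of the brief intervention in general, which is how Method of Measurement frames the outcome. The reported validity of the tool does not settle the matter either, since the protocol does not address scores obtained after instruction on the same scenarios.

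A reader might infer four stronger things that the documents do not support.

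- *The answers were given away.* The protocol describes plus-delta reflection, not disclosure of the key. Feedback on the tested items is plausible, because the performance reflected on was error detection in these videos, but it is not stated.
- *Recall alone would produce a significant effect.* The inputs are assumed, and the low end of the range has power of only 0.32 to 0.85 before clustering.
- *A positive result could support no conclusion about effectiveness.* It could still support one about the debriefed videos. What it cannot do is distinguish recall from transferable learning.
- *The problem is as strong at nine months as on the first day.* Forgetting makes recall a weaker rival at T3 and T4. It is not excluded there, because the videos are the same.

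**Conclusion.** The concern holds as a limit on interpretation. One arm receives expert discussion of all three test videos, and those videos with the same key form the whole outcome at T2, T3 and T4. An arm difference could reflect recall of that discussion, transferable learning or both, and nothing in the described design or analysis tells them apart. This conclusion rests on the text alone. The size does not: 0.05 to 0.30 on the 0-1 score depends on assumed values of p and r at T2, and significance depends further on an assumed SD and intracluster correlation.

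**What to change.** **Cohorts already run.** State the conclusion at T2, T3 and T4 as detection of errors in the same videos that were debriefed. Do not claim improved brief-intervention learning in general, and list recall of the debriefed videos as a possible explanation. The cost is a narrower conclusion; no data or analysis changes.

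**Any further run.** In each experimental group, leave either scenario 1 or scenario 2 out of the debriefing, and vary which one across groups. The pair is suitable because both show a patient not ready to quit. All students still watch and score all three videos at every time. Base the transfer claim on the experimental-versus-control difference on the same held-out scenario: groups with scenario 1 held out against controls' scenario 1 scores, and likewise for scenario 2. Put scenario in the model and allow for the randomised small groups. Report the debriefed scenarios separately.

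This needs no new video, staff or visit. The downsides to state are:

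- lower precision, because the transfer claim rests on one scenario per student;
- an intervention that debriefs two scenarios rather than three;
- an uneven 3:2 split of the held-out scenario over five experimental groups;
- no transfer test for the ready-to-quit patient, since scenario 3 is always debriefed;
- only partial transfer, because scenarios 1 and 2 share patient type and tool, so debriefing one may cue items in the other.

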## Method of Measurement

To assess the change in learning regarding brief tobacco cessation counseling among nursing students, the Brief Tobacco Intervention BTI-St© tool was used, incorporating the standardized patient videos described earlier. This instrument is based on a criterion-referenced or competency test model, enabling an objective evaluation of students' BTI performance and identifying learning deficiencies. It is presented as an algorithm consisting of 23 dichotomous items organized according to the 5As and 5Rs model and has demonstrated adequate validity and reliability (Ramos-Morcillo et al., 2022). Students must view a recorded clinical scenario and determine whether the brief intervention criteria for smoking cessation are met. Responses are corrected according to the gold standard defined during the scenario validation, with item scores ranging from 0 (incorrect) to 1 (correct). The maximum total score for each scenario ranges from 0 to 1 point if the student answers all items correctly.

## Data Analysis

Descriptive analyses were conducted, calculating the mean and standard deviation for quantitative variables, and frequencies and percentages for qualitative variables. To compare the variables studied between the control and experimental groups, the t-Student test and Chi-Square test were used depending on the nature of the comparison variable.

The overall score of each student was calculated for each of the three cases and weighted according to the number of items they had to answer. Thus, the score in each case could range between 0 and 1. A two-factor repeated measures ANOVA was used to analyze the differences in within-subject and between-subject measures. The assumptions of this test include the condition of sphericity; if this assumption was violated, the multivariate approach, which does not require the variance-covariance matrix to be spherical, or the F statistic with modified degrees of freedom using the  $\epsilon$  correction factor (Greenhouse-Geisser estimate), was applied (Pardo Merino & San Martín Castellanos, 2011). A significance level of 5% ( $p \leq 0.05$ ) was utilized in the statistical analysis. Data analysis was performed using SPSS® v. 25 (Statistical Package for the Social Sciences).

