## PROTOCOL

### Effectiveness of Debriefing After a Short Training on Brief Tobacco Intervention for Nursing Students: A Randomized Clinical Trial

#### **Aim:**

The aim of this study was to determine the effectiveness of debriefing after objective evaluation of a brief tobacco intervention (BTI) training in nursing students, and its progression at 3 and 9 months.

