##### Sample and Setting

The study was conducted with second-year nursing students at the University of Murcia, Spain, during the 2021-2023 academic years. Inclusion criteria were being enrolled in the second-year course "Bases de Enfermería Comunitaria," where BTI training is provided, and agreeing to participate in the study. In the two academic years during which the research was conducted, 300 students were enrolled. The sample size was calculated using Pass 11 (Power Analysis & Sample Size) software for repeated measures ANOVA. For a repeated measures design with 1 between-factor and 1 within-factor, with 2 groups and 65 subjects each (total 130 subjects), each subject was measured 5 times. This design achieves 100% power to test the AB interaction if a Geisser-Greenhouse Corrected F Test is used with a 5% significance level and the actual effect standard deviation is 1.

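### Three scenario scores are calculated, but the plan does not say which one enters the ANOVA, how many scenarios must be significant, or how the 5% level is shared among them

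*Combined protocol and SAP*

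**What the plan says.** All references are to the combined protocol and SAP.

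- **Outcome.** Data Analysis: "The overall score of each student was calculated for each of the three cases". The weighting by number of items that follows puts each case on a 0-1 scale; it does not pool the cases. Method of Measurement agrees: "The maximum total score for each scenario ranges from 0 to 1 point if the student answers all items correctly".
- **Scenarios.** Developmental Process: "The scenarios included the patient was not ready to quit smoking (scenarios 1 and 2) and was ready to quit (scenario 3". All three are viewed at each of the five measurements.
- **Model.** Data Analysis: "A two-factor repeated measures ANOVA was used to analyze the differences in within-subject and between-subject measures". Sample and Setting describes the same structure, "For a repeated measures design with 1 between-factor and 1 within-factor", with two groups and five measurements.
- **Level.** Data Analysis sets 5% for the statistical analysis and mentions no adjustment.
- **Aim.** One question: "to determine the effectiveness of debriefing after objective evaluation of a brief tobacco intervention (BTI) training in nursing students", with progression at 3 and 9 months. No scenario or score is named.

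No section defines a total or mean over the scenarios, ranks them, or says how mixed results would be read.

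**The concern.** Group and time use up both factors of the ANOVA, so scenario has no place in the model. With three scores and no rule for combining them, the natural reading is one group by time ANOVA per scenario, each at 5%. That is an inference; the plan does not state it.

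On that reading, a single conclusion about debriefing could rest on whichever scenario reached significance, and its error rate would not be the stated 5%. Mixed results are plausible, because two scenarios show a patient not ready to quit and one shows a patient who is ready. The plan gives a reader no way to tell whether one positive scenario out of three counts as success.

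**Working it through.** **The plan's own figure.** Sample and Setting gives 100% power for one group by time interaction: 2 x 65 students, 5 measurements, effect SD 1, 5% level. The within-cell SD (σ), the correlation between measurements (ρ) and the score concerned are not given, so the figure cannot be reproduced uniquely. The noncentrality is λ = ε·N·T·(effect SD)²/[σ²(1−ρ)], where ε is the sphericity factor. With N = 130, T = 5, ε = 1 and ρ = 0:

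- σ = 1: λ = 650/1 = 650, power about 100%.
- σ = 2: λ = 650/4 = 162.5, power about 100%.
- σ = 10: λ = 650/100 = 6.5, power about 50%.

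The statement is consistent with 100% at an assumed σ of 1 or 2. It concerns a single test and does not settle which score is meant.

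**Inputs for the error rate.** From the documents: three scores, five measurements (so 4 df for the interaction between two groups and time), and a 5% level. Assumed: correlation r between scenario scores, since none is given; independent students; no true effect.

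**Any one scenario suffices.** With r = 0, P(at least one) = 1 − 0.95³ = 0.143. For other r, three equally correlated 4-df chi-square statistics were simulated (1,000,000 draws), each compared with the 5% critical value.

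**All three needed.** With r = 0, 0.05³ = 0.000125, about 0.01%. Simulation at r = 0.95 gives 2.8%.

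**One pre-specified score.** 5% by construction.

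**Holm, any scenario.** When no scenario has an effect, Holm makes a false claim only if the smallest p-value is at or below 0.05/3 = 0.0167. With r = 0 this gives 1 − (1 − 0.0167)³ = 0.049.

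| Assumed r | Any of three, unadjusted | Any of three, Holm |
|---|---|---|
| 0 | 14.3% | 4.9% |
| 0.5 | 12.9% | 4.6% |
| 0.9 | 8.6% | 3.1% |
| 0.95 | 7.5% | 2.7% |

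The unadjusted rate tends to 5% as r nears 1. A simulated mixed ANOVA with the Greenhouse-Geisser correction, 80 against 65 students and compound symmetry gave 13.8%, 12.9%, 8.8% and 7.5% in the same order.

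**Power.** A noncentrality of 11.94 gives a 4-df test 80% power at 5% and 66% at 1.67%. If the same effect is present in all three scenarios, the chance that at least one is significant under Holm is 92%, 88% or 84% at r = 0.3, 0.5 or 0.7. For the mean of the three scores, with equal variances and correlations, the noncentrality is 11.94/[(1 + 2r)/3] for a common effect, and one ninth of that for an effect in one scenario:

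| Assumed r | Mean score, common effect | Mean score, one scenario only |
|---|---|---|
| 0.3 | 98% | 21% |
| 0.5 | 94% | 17% |
| 0.7 | 89% | 15% |

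**The case against.** The strongest reply is that the inflation needs two steps the plan never takes. First, three ANOVAs must have been run; the text has one ANOVA in the singular, speaks of an overall score, and powers one interaction. If a single score was analysed, this multiplicity does not arise. Second, one significant scenario must be enough. If all three were required, the false-positive rate would be below 5%.

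Both points stand as limits on the size of the problem. A reader might infer that the trial's error rate was 7-14%. The documents do not support that, because they state neither the number of tests nor the success rule.

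The reply does not close the gap. The overall score is defined case by case, and no single score is defined anywhere. If one was used, the reader cannot tell which. If three were used, nothing says how they lead to one conclusion. The missing definition remains on either reading.

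A reader might also infer that Holm would secure a 5% level. It would not do so alone: Developmental Process states that "The unit of randomization was small groups (13-16 students/group"), and Data Analysis has no term for those groups. That is a separate matter.

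**Conclusion.** The concern holds in this form: the score analysed, the success rule and the handling of three scores at one 5% level are all undefined. That omission is plain from the text.

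Its numerical size is conditional. The rate is about 14% down to 7.5% (r from 0 to 0.95) if three tests were run and any one suffices, about 0.01% to 2.8% if all three were needed, and 5% with one pre-specified score. These figures assume independent students, equal correlations between scenarios and no true effect; the correlations are not from the documents. Correction is worthwhile because it is cheap and tells the reader what the claim rests on.

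**What to change.** In Data Analysis:

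1. State that each of the three scenario scores is tested for the group by time interaction.
2. Apply Holm across the three tests (ordered p-values against 0.05/3 = 0.0167, 0.05/2 = 0.025 and 0.05) and report all three adjusted p-values.
3. Report the group differences at T2, T3 and T4 as descriptive estimates with confidence intervals, because the omnibus interaction has no direction. They should not become further tests. Three scenarios by three times is nine comparisons; tested unadjusted, they would give about 19-32% for at least one false positive (assumed scenario correlation 0.5-0.9, time correlation 0.3-0.6, independent students). For the same reason, say whether the planned t-tests between groups include the outcome scores.
4. Label the rule post hoc if results have been seen.
5. Note that Holm does not secure a 5% level unless the analysis also accounts for the small groups randomised.

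Naming the mean of the three scores as the single primary outcome is an alternative choice, not a correction. It does better for an effect common to all scenarios and much worse for an effect in one, and it gives two-thirds of the weight to patients not ready to quit.

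**Cost.** A few sentences and three adjusted p-values, with no new data. Power for an effect confined to one scenario falls from 80% to about 66% at Holm's first step. The plan is written in the past tense; a rule added after results were seen improves disclosure but does not restore error control. Accounting for the small groups is a larger change with its own power cost.

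### The planned tests do not tie any arm comparison to T2, T3 or T4, so they cannot show when debriefing worked or whether its effect lasted to 3 and 9 months

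*Combined protocol and SAP*

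**What the plan says.** The Aim covers the effectiveness of debriefing "and its progression at 3 and 9 months".

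Developmental Process places the first two measurements around the shared training ("At baseline, before BTI training (T0); followed by training in BTI in Primary Care (T1"). It then continues: "Subsequently, in the experimental group, an expert instructor conducted a structured debriefing". Controls received nothing further. T2 closes the first day; T3 and T4 follow at three and nine months.

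Sample and Setting describes a design "with 2 groups and 65 subjects each (total 130 subjects), each subject was measured 5 times" and says: "This design achieves 100% power to test the AB interaction". No other test has a power statement.

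Data Analysis says: "A two-factor repeated measures ANOVA was used to analyze the differences in within-subject and between-subject measures", with a sphericity fallback and a 5% level. That this ANOVA spans all five times is inferred from Sample and Setting. Data Analysis also says: "To compare the variables studied between the control and experimental groups, the t-Student test and Chi-Square test were used", and on the outcome: "The overall score of each student was calculated for each of the three cases". It names no primary score or time, no contrast at T2, T3 or T4, no change from T1, no follow-up procedure and no multiplicity rule.

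**The concern.** The arms are handled alike up to and including T1, so the aim concerns differences at three particular times: T2 for the immediate effect, T3 and T4 for its persistence. The named ANOVA gives global tests.

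- A significant interaction says that the arm difference is not constant over the five times. It does not say where the difference lies, and a gap at T0 and T1 that later closes can also produce it.
- The between-subject test averages two scores that debriefing cannot have touched with three that it can.

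Means by arm and time, if reported, would describe the pattern without testing it. With no contrast fixed, the time points and scores to stress could be chosen after the data are seen, and a claim that the benefit persists at 9 months would have no planned test behind it.

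**Working it through.** **Inputs from the documents.** Power statement: 65 per arm, 5 measurements, effect SD 1, 5% level (Sample and Setting). Allocation: 80 and 65 students in five small groups per arm, taken here as groups of 16 and 13 (Developmental Process). Three case scores (Data Analysis).

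**Assumptions, since the documents give no values.** Outcome SD 1, equal correlation ρ = 0.5 between times, arm difference 0.4 SD where present, complete data. For clustering, residual intraclass correlation (ICC) 0.05, range 0.01-0.10.

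**1. The plan's own figure.** With noncentrality λ = N·T·σm²/[σ²(1−ρ)] = 130 × 5 × 1/(1 × 0.5) = 1300 on 4 and 512 df, power is 1.00. It stays at 1.00 for outcome SDs from 0.1 to 2. The stated 100% reproduces, but it concerns the interaction alone.

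**2. Between-subject test, clustering ignored.** A sustained effect d contributes (0 + 0 + d + d + d)/5 = 0.6d, which is 0.24 for d = 0.4. The five-time mean has variance (1 + 4 × 0.5)/5 = 0.6. With h = 80 × 65/145 = 35.86, the noncentrality is 0.24 × √(35.86/0.6) = 1.86 on 143 df: power 45%.

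**3. Interaction by pattern, clustering ignored.** λ = h·Σ(d − mean d)²/(1−ρ) on 4 and 572 df.

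| Arm difference of 0.4 SD at | Σ(d − mean d)² | λ | Power |
|---|---|---|---|
| T2, T3, T4 | 2 × 0.24² + 3 × 0.16² = 0.192 | 13.77 | 86% |
| T2, T3 only | 0.192 | 13.77 | 86% |
| T3, T4 only | 0.192 | 13.77 | 86% |
| T0, T1 only (no later difference) | 0.192 | 13.77 | 86% |
| T2 only, or T4 only | 4 × 0.08² + 0.32² = 0.128 | 9.18 | 67% |

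The exact equality of the first four rows depends on equal correlation. Under a first-order autoregressive correlation of 0.7, the multivariate test gives 71%, 93% and 71% for the first three. Under either structure, the F test does not identify the pattern.

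**4. If the t-test sentence covers the scores.** Three cases at three post-debriefing times are 9 tests. Familywise error is 1 − 0.95⁹ = 37.0% if independent, and about 33% to 20% at correlations of 0.3 to 0.7. One score at three times gives 1 − 0.95³ = 14.3%.

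**5. Named contrasts against the global tests, all on the clustered basis.** The design factor is k = (1 + 15 × 0.05)/80 + (1 + 12 × 0.05)/65 = 0.0219 + 0.0246 = 0.0465.

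- One time, adjusted for T0 and T1: residual variance 0.667, SE = √(0.667 × 0.0465) = 0.176, noncentrality 0.4/0.176 = 2.27 on 8 df. Power is about 51% (68% to 39% over the ICC range).
- The same contrast with Holm across three times: about 37% at each time for a sustained effect (simulation). With no effect anywhere, familywise error is 4.8%.
- Interaction, sustained effect: λ = 0.192/(0.5 × 0.0465) = 8.26 on 4 and 32 df (approximate group-mean version). Power is about 55%.
- Between-subject test: 0.24/√(0.6 × 0.0465) = 1.44 on 8 df. Power is about 25%.
- Change from T1 at one time: variance 2 × (1 − 0.5) = 1, noncentrality 0.4/√0.0465 = 1.86 on 8 df. Power is about 37%.

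**The case against.** The strongest reply is that the plan already compares the arms. The t-test sentence refers to the variables studied, and the tool scores are quantitative variables under study. It may therefore cover scores by visit, although it could equally describe baseline comparability; the text does not settle this. A reader might infer that no arm comparison of scores was planned at all, and the documents do not support that. What stands is narrower: no comparison is tied to a time, a score, an adjustment or an error rule. If the t-tests do cover the scores, the gap becomes one of uncontrolled multiplicity.

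A second reply is that the interaction is a legitimate test, commonly followed by simple effects, and that means and SDs are planned. The first part is right. A reader might infer that the ANOVA is invalid; it is not, as a global test with arms balanced before debriefing. But no follow-up step is stated.

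Other inferences also go too far. Counting 15 tests (three cases at five times) overstates the relevant family, because T0 and T1 cannot carry a debriefing effect. Setting 86% for the interaction beside 51% for one contrast mixes an unclustered figure with a clustered one; the like-for-like figures are about 55% and 51%. And the interaction is not equally powerful for every pattern: an effect at T2 alone gives 67%.

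**Conclusion.** The concern holds as a gap in specification. From the text alone, only T2, T3 and T4 can carry the effect, the only powered test is the five-time interaction, and no contrast at those times is defined. Followed as written, the named tests cannot answer the 3- and 9-month part of the aim. The factor of 0.6 for the between-subject test is arithmetic and needs no assumption beyond a sustained effect. The 37% familywise error is an upper-end figure: it requires the t-tests to be meant for all three case scores at T2-T4 and to be independent. The power figures are illustrative, resting on the assumed 0.4 SD effect, correlation and ICC. A reader might expect named contrasts to raise power; on the same clustered basis they do not. The plan should be amended, but the global test need not be discarded.

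**What to change.** - Name one primary score, for example the mean of the three case scores, with the separate case scores secondary. This also settles the multiplicity across cases.
- Model T2, T3 and T4 as outcomes with T0 and T1 as covariates, allowing for the ten randomised small groups with small-sample degrees of freedom (about 8). Clustering is a separate matter, but these contrasts need it for correct standard errors.
- Report the adjusted arm difference with a confidence interval at each of the three times, and apply Holm across them at 5%. Holm lets early, lasting and late effects all be declared. Testing T2 first as a gate would declare a late-only 0.4 SD effect about 2% of the time at each of T3 and T4, against about 33% with Holm.
- Give arm differences in change from T1 as a sensitivity analysis, because covariate adjustment does not fully remove a true T1 gap. Keep the five-time ANOVA as a supporting global test.
- State what the t-test sentence covers. The protocol is written in the past tense, so label the contrasts post hoc if results have been seen.

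The cost is a little more analysis and lower power per time point: about 51% unadjusted and about 37% with Holm, against about 55% for the interaction, all at ICC 0.05. The Holm loss is smaller if fewer times are tested, but the aim needs all three. No new data are required, since T0 and T1 are already part of the measurement schedule.
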